### *Imputation of missing data during the on-treatment period*

Missing DLco values during the on-treatment period will be imputed from other on-treatment measurements assuming MAR, using SAS® PROC MI.

Only DLco values collected during the on-treatment period will be included in the imputation model. This way, missing DLco values during the on-treatment period will be imputed based solely on observed on-treatment calculated DLco values.

The imputation model will include baseline DLco, baseline age and all observed DLco values at weeks 26 and 52 and will be stratified by treatment group of placebo and olipudase alfa. Since the

pattern of missing data could be non-monotone, a MCMC method will be used. A minimum value of 0 will be specified in order to avoid negative imputed DLco values.

Sample SAS code is provided below:

```
proc mi data=DATAIN out=DATAOUT nimpute=100 minimum=0;  
  var DLCO_BASE AGE_BASE DLCO_W26 DLCO_W52;  
  by TRTPN;  
run;
```

For the splenomegaly-related score endpoint which is collected at Weeks 14, 26, 38 and 52, the above code will be modified accordingly.

As stated above, the input dataset DATAIN will include only DLco values collected during the on-treatment period. Any DLco values collected after the treatment discontinuation (after last infusion +13 days) will be excluded from the input dataset. In practice, the MI procedure will generate imputed values for all missing values (whether on-treatment or post-treatment), but only imputed values during the on-treatment period will be kept in the final datasets that will be analyzed using ANCOVA. Imputed values during the post-treatment period will be discarded and replaced by imputed values described in the next section.

### ***Imputation of missing data after treatment discontinuation***

Missing DLco values during the post-treatment period will be imputed assuming DLco values will, on average, return to baseline values.

For each patient, missing post-treatment DLco values will be imputed 100 times, using a random draw from a normal distribution, with mean equal to a patient's own baseline value and variance equal to the conditional variance at the specific time-point, given the baseline value.

Let  $Y_0$  and  $Y_1$  denote the DLco at baseline and at the specific time-point respectively. Since  $Y_0$  and  $Y_1$  are assumed to have a bivariate normal distribution, the conditional variance of  $Y_1$  given  $Y_0$  is:

$$Var(Y_1|Y_0 = y_0) = \sigma_1^2(1 - \rho^2)$$

where denotes the variance of  $Y_1$  and  $\rho$  the coefficient of correlation between  $Y_0$  and  $Y_1$ .

The conditional variance will be estimated from observed data within the same treatment arm at the specific time-point.

During the random generation process, a minimum value of 0 will also be applied in order to avoid negative imputed DLco values.

### **3 INTERIM ANALYSIS**

There is no formal interim analysis before the primary timepoint (Week 52). Periodic unblinded safety data review is carried out by an external Data Monitoring Committee, aided by external vendor providing statistics and programming support. Efficacy will be assessed when all patients complete 52 weeks in PAP and data are unblinded to the study team in preparation for the CSR for PAP. For ETP data, efficacy analysis is exploratory.

## **4 DATABASE LOCK**

The database is planned to be locked within 6 weeks after the last patient last visit in PAP.

## **5 SOFTWARE DOCUMENTATION**

All summaries and statistical analyses will be generated using SAS Version 9.0 or higher. The exact version used will be documented in the clinical study report.

## 7 LIST OF APPENDICES

### 7.1 FACIT-DYSPNEA SHORT FORM - CONVERSION FROM RAW TO SCALE SCORES

Raw dyspnea score	Scale score	SE	Raw functional limitations score	Scale score	SE
0	27.7	4.7	0	29.7	4.7
1	32.8	3.7	1	34.9	3.4
2	36.1	3.2	2	38.0	3.0
3	38.6	2.8	3	40.3	2.7
4	40.6	2.6	4	42.1	2.5
5	42.3	2.4	5	43.8	2.4
6	43.8	2.2	6	45.2	2.3
7	45.2	2.2	7	46.5	2.2
8	46.4	2.1	8	47.8	2.2
9	47.6	2.1	9	49.0	2.2
10	48.8	2.0	10	50.1	2.1
11	50.0	2.0	11	51.2	2.1
12	51.1	2.0	12	52.3	2.1
13	52.1	1.9	13	53.4	2.1
14	53.2	1.9	14	54.4	2.0
15	54.2	1.9	15	55.4	2.0
16	55.2	1.9	16	56.4	2.0
17	56.2	1.9	17	57.4	2.0
18	57.2	1.9	18	58.4	2.0
19	58.1	1.9	19	59.4	2.0
20	59.2	1.9	20	60.4	2.1
21	60.2	2.0	21	61.4	2.1
22	61.2	2.0	22	62.4	2.1
23	62.3	2.0	23	63.5	2.2
24	63.5	2.1	24	64.7	2.2
25	64.8	2.1	25	66.0	2.3
26	66.1	2.3	26	67.3	2.4
27	67.7	2.4	27	68.9	2.6
28	69.5	2.6	28	70.7	2.8
29	71.9	3.0	29	73.0	3.2
30	75.9	4.0	30	76.7	4.1

## 7.2 POTENTIALLY CLINICALLY SIGNIFICANT ABNORMALITIES CRITERIA

### Liver function tests

ALT	>3 x ULN >5 x ULN >10 x ULN >20 x ULN
AST	>3 x ULN >5 x ULN >10 x ULN >20 x ULN
Alkaline Phosphatase	>1.5 x ULN
Total Bilirubin	>1.5 x ULN >2 x ULN
ALT and Total Bilirubin	ALT >3 x ULN and Total Bilirubin >2 x ULN

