7.2 EXCLUSION CRITERIA

Patients who have met all the above inclusion criteria listed in [Section 7.1](#) will be screened for the following exclusion criteria:

- E 01. The patient has received an investigational drug within 30 days before study enrollment.
- E 02. The patient has a medical condition, including significant intercurrent illness; significant cardiac disease (eg, clinically significant arrhythmia, moderate or severe pulmonary hypertension or clinically significant valve dysfunction, or $<40\%$ left ventricular ejection fraction by echocardiogram ECHO); active hepatitis B or hepatitis C, or infection with human immunodeficiency virus (HIV); malignancy diagnosed within the past 5 years (other than non-melanoma skin cancer), or any other serious medical condition that may preclude participation in the study.
- E 03. The patient has a platelet count $<60 \times 10^3/\mu\text{L}$ based on the average of 2 samples.
- E 04. The patient has an international normalized ratio (INR) >1.5 .

- E 05. The patient has alanine aminotransferase (ALT) or aspartate aminotransferase (AST) >250 IU/L or total bilirubin >1.5 mg/dL (except for patients with Gilbert's syndrome).
- E 06. The patient has had a major organ transplant (eg, bone marrow or liver).
- E 07. The patient is scheduled during the study for in-patient hospitalization including elective surgery and excluding the liver biopsies required per protocol.
- E 08. The patient, in the opinion of the investigator, is unable to adhere to the requirements of the study.
- E 09. The patient is unwilling or unable to abstain from the use of alcohol for 1 day before and 3 days after each study drug infusion. Testing for blood alcohol levels will not be required.
- E 10. The patient is unwilling or unable to avoid 10 days before and 3 days after the protocol scheduled liver biopsies, that are required at screening/baseline, at Week 52 and at Week 104, the use of medications or herbal supplements that are potentially hepatotoxic (eg, 3-hydroxy-3-methyl glutaryl coenzyme A reductase inhibitors, erythromycin, valproic acid, anti-depressants, kava, echinacea) and/or may cause or prolong bleeding (eg, anti-coagulants, ibuprofen, aspirin, garlic supplements, ginkgo, ginseng).
- E 11. The patient requires medications that may decrease olipudase alfa activity (eg, fluoxetine, chlorpromazine, tricyclic antidepressants [eg, imipramine, or desipramine]).
- E 12. The patient requires use of invasive ventilatory support.

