Because skeletal involvement can lead to osteopenia or osteoporosis, common manifestations of ASMD and splenomegaly have been shown to be inversely correlated with lumbar spine bone mineral density Z-scores (30), the severity of bone disease will be measured at baseline and once every year. A biomarker for bone resorption, C-telopeptide concentrations in serum have been shown to be decreased in patients with Gaucher disease.

Although hemoglobin level, platelet count, and white blood cell count will comprise part of the standard safety laboratory assessments, these parameters are often abnormal in patients with ASMD because many cells of the reticuloendothelial system originate in the bone marrow and it is one of the most extensively involved organs in ASMD (31, 32). Bone marrow involvement, combined with hypersplenism, contributes to the thrombocytopenia, anemia, and to the neutropenia sometimes observed in patients with ASMD.

Biomarkers will be measured that are known to be associated with macrophage proliferation (ACE), secreted by activated (NP cells) macrophages (chitotriosidase and CCL18), and

inflammatory background triggered in sphingolipidoses (bone-specific alkaline phosphatase, C-telopeptide). Changes in these biomarkers have supported the clinical responses observed with enzyme-replacement and substrate-reduction therapies in other sphingolipidoses such as Gaucher disease Type 1 and Fabry disease (33, 34, 35). The initial objective to monitor ACE changes through 52 weeks of treatment for all patients has been achieved; no further longitudinal analysis is required after the cutoff date for a planned second database lock of the study for purpose of regulatory submissions in 2021. CCL18 and chitotriosidase will continue to be monitored to assess overall disease burden.

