##### ***General common rules***

All safety analyses will be performed on the safety population as defined in [Section 2.3.2](#), unless otherwise specified, using the following common rules:

- The baseline value is defined as the last available value before the first infusion of the study drug, except for hematology parameters and possibly ECG parameters. For complete definition of baseline, refer to [Section 2.6.1](#).
- The analysis of the safety variables will be essentially descriptive and no systematic testing is planned.

The potentially clinically significant abnormality (PCSA) values are defined by the Sponsor according to predefined criteria/thresholds based on literature review for clinical laboratory tests, vital signs, and ECG; this list is provided in [Section 7.2](#).

- PCSA criteria will determine which patients had at least 1 PCSA during the treatment-emergent adverse event period, taking into account all evaluations performed during the treatment-emergent adverse event period, including unscheduled or repeated evaluations. The number of all patients with any post-baseline evaluation will be the numerator for the on-treatment PCSA percentage.
- The treatment-emergent PCSA denominator by group for a given parameter will be based on the number of patients assessed for that given parameter in the treatment-emergent adverse event period by treatment group on the safety population.
- Before determining a value as PCSA, the value will be rounded to the precision that the PCSA criterion is defined.

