### Hematology

WBC	<3.0 GIGA/L (non-Black), <2.0 GIGA/L (Black), >=16.0 GIGA/L
Lymphocytes	>4.0 GIGA/L
Neutrophils	<1.5 GIGA/L (non-Black) <1.0 GIGA/L (Black)
Monocytes	>0.7 GIGA/L
Basophils	>0.1 GIGA/L
Eosinophils	>0.5 GIGA/L or > ULN if ULN >=0.5 GIGA /L
Hemoglobin	Males: <=115 g/L (<=7.14 mmol/L) and 20% decrease from baseline; >=185 g/L (>=11.48 mmol/L) Females: <=95 g/L (<=5.9 mmol/L) and 20% decrease from baseline; >=165 g/L (>=10.24 mmol/L)  Decrease from Baseline >=20 g/L (1.24 mmol/L)
Hematocrit	Males: <=0.37 v/v and 20% decrease from baseline; >=0.55 v/v Females: <=0.32 v/v and 20% decrease from baseline; >=0.5 v/v
RBC	>=6 TERA/L
Platelets	<100 GIGA/L and 20% decrease from baseline >=700 GIGA/L

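### Several laboratory PCSA cut-offs in the SAP have no baseline term, so patients who enter already beyond a cut-off count as treatment-emergent and dilute the between-arm contrast

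*SAP*

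**What the plan says.** SAP 7.2 (Liver function tests) gives ALT and AST the tiers ">3 x ULN >5 x ULN >10 x ULN >20 x ULN". Alkaline phosphatase, total bilirubin and the combined ALT/bilirubin row are likewise multiples of ULN. Under Hematology, WBC is "<3.0 GIGA/L (non-Black), <2.0 GIGA/L (Black), >=16.0 GIGA/L". Neutrophils, lymphocytes, monocytes, basophils and eosinophils also have cut-offs without a change from baseline. In the same table the low platelet criterion is "<100 GIGA/L and 20% decrease from baseline", and low hemoglobin and hematocrit carry the same 20% condition.

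The counting rule is in SAP 2.4.6 (General common rules): "PCSA criteria will determine which patients had at least 1 PCSA during the treatment-emergent adverse event period". The denominator is "based on the number of patients assessed for that given parameter in the treatment-emergent adverse event period by treatment group on the safety population". Neither uses baseline PCSA status.

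On entry, Protocol 7.2 (E 05) excludes patients with "alanine aminotransferase (ALT) or aspartate aminotransferase (AST) >250 IU/L", so values up to that limit are allowed. The same criterion limits total bilirubin but exempts patients with Gilbert's syndrome. No exclusion criterion sets a WBC or neutrophil floor. Protocol 9.7 says that marrow involvement with hypersplenism "contributes to the thrombocytopenia, anemia, and to the neutropenia sometimes observed in patients with ASMD".

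**The concern.** A treatment-emergent count should measure what happened after treatment began. Here it also includes abnormalities that the patient brought into the trial. The protocol expects such patients: besides the text on neutropenia, the rationale for protocol amendment 08 says the DLT rules were changed because patients may enter with abnormal liver tests due to ASMD. Within SAP 7.2, platelets, hemoglobin and hematocrit already have the corresponding safeguard on the low side.

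What is at stake is how the by-arm safety tables read. Transaminase elevation during dose escalation was later named an important identified risk (Appendix C, amended protocol 13). Improvement in ALT and AST is also an efficacy endpoint (SAP 2.1.4.3). Yet a patient who falls from 6 x to 4 x ULN on treatment appears as a treatment-emergent PCSA.

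**Working it through.** The plan states no figure for the PCSA tables, so there is nothing to reproduce. The check has three parts.

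**1. Which ALT/AST tiers can be occupied at entry.** Inputs: the 250 IU/L limit (Protocol 7.2) and an assumed ULN of 30–60 IU/L. A patient at the limit sits at 250/ULN.

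| Assumed ULN (IU/L) | 250/ULN | 3 x ULN | 5 x ULN | 10 x ULN | 20 x ULN |
|---|---|---|---|---|---|
| 30 | 8.3 | 90 | 150 | 300 | 600 |
| 40 | 6.25 | 120 | 200 | 400 | 800 |
| 50 | 5.0 | 150 | 250 | 500 | 1000 |
| 60 | 4.2 | 180 | 300 | 600 | 1200 |

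The >3 x tier can be occupied at entry for every ULN in the range. The >5 x tier can be occupied only if ULN is below 50. The >10 x tier starts at 300 IU/L or more and the >20 x tier at 600 or more, so nobody within the entry limit is in either. For low WBC and neutrophils nothing at entry prevents a baseline value beyond the cut-off.

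**2. How readily a stable patient is counted.** One value suffices. Protocol 1.2.1.1 schedules liver tests before infusion and 24 and 48 hours after it at Weeks 0, 2, …, 16. That is 9 x 3 = 27 samples, of which 26 follow the start of treatment. A patient who stays at 4 x ULN is certain to be counted.

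**3. Effect on the arm comparison.** Let *b* be the share beyond the cut-off at baseline and again at least once on treatment, taken as equal in both arms. Let *r* be the rate of new crossings among the rest. The tabulated rate is b + (1 − b)r, so the difference between arms shrinks to (1 − b) times its value among patients not beyond the cut-off at baseline. With assumed r = 5% (placebo) and 30% (olipudase alfa):

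| b | Placebo | Olipudase alfa | Difference (points) | Ratio |
|---|---|---|---|---|
| 0% | 5% | 30% | 25 | 6.0 |
| 10% | 14.5% | 37% | 22.5 | 2.6 |
| 20% | 24% | 44% | 20 | 1.8 |
| 30% | 33.5% | 51% | 17.5 | 1.5 |
| 40% | 43% | 58% | 15 | 1.35 |

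For b = 20%: placebo 0.20 + 0.80 x 0.05 = 0.24; olipudase alfa 0.20 + 0.80 x 0.30 = 0.44. With 18 patients per arm, 20% is 3.6 patients. Restricting numerator and denominator to patients not beyond the cut-off at baseline returns 5% versus 30% at every b.

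**The case against.** A reader might infer that drug-related liver elevations are masked and that the safety output cannot separate drug from disease. The documents do not support that.

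- **Baseline-relative liver rules exist and are reported.** Rises above 3 x baseline and ULN, and above 3 x ULN with more than 2 x baseline plus symptoms, are AESIs (SAP 2.1.5.1). They have listings (Protocol 11.5.5.1) and narratives (SAP 2.5). They are also DLT criteria (Protocol 8.1.4), and DLTs are a line in the TEAE overview (SAP 2.4.6.1.1).
- **They reach the AE tables.** Protocol 10.4.2 has laboratory values that meet an AESI definition recorded as AEs. SAP 2.4.6.13 repeats the TEAE overview and the SOC/PT table by baseline ALT/AST status.
- **Change is summarized.** SAP 2.4.6.2 covers change and percent change for liver tests and hematology, with PCSA listings. SAP 2.4.5.7 adds an MMRM on percentage change in pre-infusion ALT and AST.
- **The tiers help.** A rise from 3 x to 6 x ULN shows as a new entry in the >5 x tier.
- **The excess survives.** Suppose 4 of 18 per arm start beyond the cut-off, and 3 of the other 14 on olipudase alfa newly cross against none of 14 on placebo. The table prints 7/18 (39%) versus 4/18 (22%), and the three-patient excess is still visible.
- **The tables are descriptive**, with no systematic testing planned, and the trial is small enough to read listings.

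Most of this stands for ALT and AST, but the cover is partial. The AESI tables in SAP 2.4.6.1.2 are for infusion-associated reactions; the DLT line mixes liver and other events; the MMRM uses pre-infusion values at quarterly visits only; and change summaries do not count patients who newly cross a threshold. For low WBC and neutrophils there is no baseline-relative AESI. The shift tables use below/normal/above, so they cannot show a further fall in a patient already low.

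**Conclusion.** The point holds as a fault in the PCSA tables. For every laboratory parameter whose cut-off has no baseline term, a stable or improving patient already beyond the cut-off is labelled treatment-emergent, and the between-arm contrast is diluted by the factor (1 − b) on the difference scale. For ALT/AST this is confined to the >3 x ULN tier, plus the >5 x tier if ULN is below 50 IU/L. It would be wrong to extend it to all four tiers. The gap is larger for low WBC and neutrophils, where the concern is a further fall.

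The size is not known. ULN, the share beyond a cut-off at baseline and the new-crossing rates are all assumptions; the documents say only that neutropenia occurs in some patients. Keeping the upper ALT/AST tiers clear also assumes that values stay within the entry limit between screening and the first infusion. The numerator is taken as patients with at least one PCSA, as in Protocol 11.5.5; the SAP's separate sentence describing the numerator is a different matter. This is a cheap, worthwhile improvement rather than a threat to the safety conclusions.

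**What to change.** In SAP 2.4.6 and 7.2, keep the overall PCSA row and add a split by baseline PCSA status for every laboratory parameter whose cut-off has no baseline term:

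- **Not beyond the cut-off at baseline:** restrict both numerator and denominator to these patients.
- **Already beyond the cut-off at baseline:** show them on a separate row, with any move to a higher tier where tiers exist.

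This uses data already collected and changes no threshold or clinical rule. The cost is SAP wording, a row split in the PCSA tables, and smaller denominators in each row, which matters with about 18 patients per arm.

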### Hematology

WBC	<3.0 GIGA/L (non-Black), <2.0 GIGA/L (Black), >=16.0 GIGA/L
Lymphocytes	>4.0 GIGA/L
Neutrophils	<1.5 GIGA/L (non-Black) <1.0 GIGA/L (Black)
Monocytes	>0.7 GIGA/L
Basophils	>0.1 GIGA/L
Eosinophils	>0.5 GIGA/L or > ULN if ULN >=0.5 GIGA /L
Hemoglobin	Males: <=115 g/L (<=7.14 mmol/L) and 20% decrease from baseline; >=185 g/L (>=11.48 mmol/L) Females: <=95 g/L (<=5.9 mmol/L) and 20% decrease from baseline; >=165 g/L (>=10.24 mmol/L)  Decrease from Baseline >=20 g/L (1.24 mmol/L)
Hematocrit	Males: <=0.37 v/v and 20% decrease from baseline; >=0.55 v/v Females: <=0.32 v/v and 20% decrease from baseline; >=0.5 v/v
RBC	>=6 TERA/L
Platelets	<100 GIGA/L and 20% decrease from baseline >=700 GIGA/L

### ECG – PCSA criteria

HR	<=50 bpm and decrease from baseline >=20 bpm >=120 bpm and increase from baseline >=20 bpm								
PR	>=200 ms and increase from baseline >=20 ms								
QRS	>=120 ms								
QTc	Absolute values (ms) 
 
 Males	Females	
 
 431-450ms	451-470 ms	
 
 >450 ms	>470 ms	
 
 ≥500 ms	≥500 ms	
 
 Increase from baseline (Males and Females) 30-60 ms >60 ms	Males	Females	431-450ms	451-470 ms	>450 ms	>470 ms	≥500 ms	≥500 ms
Males	Females								
431-450ms	451-470 ms								
>450 ms	>470 ms								
≥500 ms	≥500 ms								

### Clinical chemistry

Creatinine	>=150 µmol/L (Adults) >=30% increase from baseline >=100% increase from baseline
Blood Urea Nitrogen	>=17 mmol/L
Chloride	<80 mmol/L >115 mmol/L
Sodium	<=129 mmol/L >=160 mmol/L
Potassium	<3 mmol/L >=5.5 mmol/L
Glucose	
Hypoglycemia	<=3.9 mmol/L and < LLN
Hyperglycemia	>=11.1 mmol/L (unfasted), >7 mmol/L (fasted)
Albumin	<=25 g/L

### Vital signs

[figure not shown]
Heart rate	<=50 bpm and decrease from baseline >=20 bpm >=120 bpm and increase from baseline >=20 bpm
Systolic BP	<=95 mmHg and decrease from baseline >=20 mmHg >=160 mmHg and increase from baseline >=20 mmHg
Diastolic BP	<=45 mmHg and decrease from baseline >=10 mmHg >=110 mmHg and increase from baseline >=10 mmHg

### Urinalysis

pH	<=4.6 >=8
----	--------------

Signature Page

dfi12712-16-1-9-sap

Approve & eSign	
Approve & eSign
